Title of the study	A randomized controlled trial of Cystoinflation to prevent bladder injury in the adhesive disease of multiple caesarean sections
Registration #	NCT04302545
ERB reg #	Reg # 216/RC/KEMU.
Document Date	March 27,2017
Principal Investigator:	[name] , FCPS; Obstetrics & Gynaecology. Assistant Professor (Obstetrics & Gynaecology), King Edward Medical University /Lady Willingdon Hospital, Lahore, Pakistan
Co-Investigators:	
 • [name], MS trainee (Obstetrics & Gynaecology), King Edward Medical University /Lady Willingdon Hospital, Lahore, Pakistan • [name], FCPS trainee (Obstetrics & Gynaecology), King Edward Medical University /Lady Willingdon Hospital, Lahore, Pakistan • [name], FCPS trainee (Obstetrics & Gynaecology), King Edward Medical University /Lady Willingdon Hospital, Lahore, Pakistan • [name], Director of Medical Education, Institute of Public Health Pakistan
Settings:	Lady Willingdon Hospital Lahore, Pakistan

Study protocol: “**A randomized controlled trial of Cystoinflation to prevent bladder injury in the adhesive disease of multiple caesarean sections**”

Project summary

Background: Repeated caesarean sections (C-section) carry the risk of bladder injury due to the formation of adhesions obscuring pelvic planes. Distension of Bladder by retrofill (Cystoinflation) is a useful technique to identify bladder margins. We hypothesize that cystoinflation can prevent bladder injury in dense adhesions of previous C-sections by improving identification of bladder outline.

Method: We will find out the effectiveness of cystoinflation by conducting a prospective randomized controlled trial in Lady Willingdon Hospital, a university-affiliated teaching hospital in Pakistan, for two years, including a follow-up period of three months. The subjects of the study will be two hundred and fourteen healthy pregnant women with previous operative deliveries which during their C-section, prove to have dense bladder adhesions. The subjects will be randomized into cystoinflation and control groups. Preoperatively, the study team will counsel the women and take informed consent to include them in the study if dense adhesions were found during their C-section. The surgeon will perform adhesiolysis after identifying bladder during retro-fill (with 300cc saline) in the cystoinflation group and without retro-fill in control. The primary outcome will be assessed by bladder injury rate, blood loss and operative time and secondary outcome by postoperative urinary tract infection, micturition problems and fistula formation. Cystoinflation will be considered effective if the proportion of bladder injury in cystoinflation group will be less than 50% of the control.

Discussion: The routine practice of preoperative insertion of urinary catheter fails to prevent bladder injury in multiple C-sections. A few scientists have successfully used cystoinflation technique to prevent bladder injury in pelvic adhesive disease. In this study, we have used cystoinflation in dense adhesions of previous C-sections. The findings of this study may support the previous studies and may serve as a trigger for ongoing research of surgical techniques to prevent iatrogenic bladder injury.

Study protocol: “A controlled study of Cystoinflation to prevent bladder injury in the adhesive disease of multiple caesarean sections”

erb registration: The institutional review board of King Edward Medical University, Pakistan
Reg # 216/RC/KEMU.

Principal Investigator: [name], FCPS; Obstetrics & Gynaecology. Assistant Professor (Obstetrics & Gynaecology), King Edward Medical University /Lady Willingdon Hospital, Lahore, Pakistan

Co-Investigators:

- [name], MS trainee (Obstetrics & Gynaecology), King Edward Medical University /Lady Willingdon Hospital, Lahore, Pakistan
- [name], FCPS trainee (Obstetrics & Gynaecology), King Edward Medical University /Lady Willingdon Hospital, Lahore, Pakistan
- [name], FCPS trainee (Obstetrics & Gynaecology), King Edward Medical University /Lady Willingdon Hospital, Lahore, Pakistan
- [name], Director of Medical Education, Institute of Public Health Pakistan

Settings: Lady Willingdon Hospital Lahore, Pakistan

Address: [name]

[contact]

Affiliated University: King Edward Medical University, Lahore, Pakistan (KEMU)

Hospital type: Government Teaching Hospital

Background

The urinary bladder injury is a rare but important complication of caesarean section (C-section). The decreasing trend of vaginal birth after C-section has led to an increased number of women with multiple C-sections.¹ After caesarean delivery, adhesions may develop between bladder and uterus (46% - 65% after primary C-section) which cause difficulty in identification and dissection of the bladder flap during the next operative delivery.^{2,3} The rate of bladder injury increases with the increasing number of C-sections being 0.13% for the first C-section, 0.09% for the second, 0.28% for the third, 1.17% for the fourth, 1.94% for the fifth, and 4.49% for the sixth caesarean delivery.⁴ The incidence of bladder perforation has been reported to be three times higher in women with the previous C-section compared to the women with first C-section (0.81% vs. 0.27%).⁵ Most bladder injuries occurred secondary to the extensive adhesive disease at the time of opening the peritoneal cavity and during the creation of the bladder flap.⁵ Bladder injury has been reported to occur with an overall incidence of 0.46% in a local Pakistani study, 0.44% in Saudi Arabia, 0.67% in Mumbai and 0.08 to 0.94% in international studies in C-section cases.⁶⁻¹¹

Tulandi and co-workers have proposed a scoring system of adhesions between bladder and uterus.¹²

Adhesions of previous C-section Between uterus and bladder	Consistency of the adhesions	<3 cm	3–6 cm	>6 cm
		Filmy	1	2
Dense	4	8	16	

Tulandi, T. & Lyell, D.J. *Gynecol Surg* (2013) 10: 25. <https://doi.org/10.1007/s10397-012-0765>

Bladder injury, although rare, has serious physical, social and psychological implications.¹³ The injury leads to prolonged operative time, urinary tract infection (UTI), micturition problems and prolonged catheterization.³ A long complicated hospital stay creates an intense feeling of helplessness and anxiety.¹³ Moreover, unrecognized bladder perforation is a leading cause of morbidity due to the development of urinary ascites, peritonitis, and fistula formation.^{14–16}

The adhesions are a major risk factor for bladder injury.¹⁷ Dye test with methylene blue is one of the methods used to identify bladder injury.³ We observed that in women with intact bladder, it made the bladder outline prominent thus improving identification of bladder outline. This observation raised the question of whether improved identification of bladder margins by bladder retro-fill (cysto-inflation) could decrease the occurrence of bladder injury in adhesions of previous C-sections.

In literature, there is insufficient evidence to support the use of cysto-inflation to prevent bladder injury. The routine practice of preoperative insertion of Foleys catheter is based on an old concept that bladder injury may occur by failure to empty the bladder preoperatively.¹⁸ The emptying of bladder improves visualization in the operative field but fails to prevent bladder injury in cases of adhesions.³ Presently, researchers are focussing on prevention of adhesion formation by the use of adhesive barriers and Aloe vera gel but evidence is still needed to prove their effectiveness.^{19,20} The omission of bladder flap formation is also under consideration but there is a lack of adequate evidence to support this method.²¹ The scientists have now started questioning the need for the routine use of an indwelling catheter.^{22–25} The studies indicate that empty bladder is ineffective to avoid bladder injury.^{22–25}

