Based on previous statistics of the target population (women with adhesions) in our hospital, about 400 subjects are expected to present during the study period. With this population, the sample size is calculated to be 107 for each group at 95% confidence level and 80% power, allowing a 10% drop out rate (Raosoft, Inc 2004; online sample size calculator for proportions). Therefore, a total of two hundred and fourteen patients fulfilling the eligibility criteria will be included in the study.

Subjects

The subjects of the study will be selected in two steps. In the first step, the women who will meet the preoperative study criteria and give the preoperative informed consent will be invited to participate in the study. In the second step, during C-section, the volunteers who will fulfil the inclusion criteria of adhesions will be enrolled in the study.

Preoperative study criteria

Inclusion criteria:

- Healthy pregnant women of any age
- Two or more previous C-sections
- Gestational age between 38-40 weeks (confirmed by dating scan)
- Provide written informed consent to participate in the study

Exclusion criteria:

- Patients with medical disorders
- Placenta previa on Ultrasonography

- Women experiencing micturition problems (dysuria, frequency, urgency, urinary retention, incontinence) before the study.
- Women who refuse to participate in the study.

The perioperative criteria of the study are

- Dense pelvic adhesions of Tulandi score 4 and above,
- adhesions covering the bladder and lower segment of the uterus so that empty bladder will not be identified among the adhesions.
- The lower segment cannot be approached without adhesiolysis.
- Adhesions will be encountered either at entry into the peritoneal cavity or before the creation of the bladder flap.
- The women with bladder injury prior to enrolment will be excluded from the study.

Recruitment procedure and consent for the study

The recruitment of subjects will be carried out over a period of 21 months (one year and nine months).

Subjects of the study will be selected in two steps.

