Control group: The subjects assigned to the control group will undergo no intervention. The Principal surgeon will perform adhesiolysis by the same traction counter-traction method with urinary catheter put on free drainage throughout the C-section.

If there will be a suspicion of bladder injury in either group, it will be confirmed by performing the retrograde dye test with methylene blue and injury will be repaired by the Principal surgeon.

Crossover

There is no possibility of crossover in this study as subjects will be selected during operation and the women who refuse to be included in either group preoperatively will be excluded from the study before group assignment.

Data collection procedure

Data will be collected at the time of admission (baseline), during surgery, on the 3rd postoperative day, at the time of discharge from the hospital and the end of three month follow-up period (for those enrolled in the study). The subjects will be advised to report for any postoperative fever or micturition problem during follow-up. Their visits will be recorded on follow up form by the study team medical officers specifically trained in correctly interpreting the problems of the subjects and filling the outcome form (See [Outcome](#) Form).

Baseline Data

The entry form will include baseline data consisting of demographic features and characteristics of the subjects recruited in the study. The demographic features will include age, gestational age, parity, socioeconomic status, and the number of previous C-sections. The other characteristics will be the score of adhesions and preoperative postmicturition bladder volume. The allotted random number will be entered in entry form of the subject and will be signed and kept in a locked place by study team manager in the theatre. (See [ENTRY FORM](#))

Outcome

Primary outcomes will be the bladder injury rate, the extent of the injury, operative time, blood loss and proportion of subjects receiving blood transfusion.

The bladder injury: The bladder injury will be detected by direct observation during surgery. The suspected bladder injury will be confirmed with the dye test and will be reported as the bladder injury rate and extent of injury.

- A. Bladder injury rate will be recorded as the percentage of subjects with bladder injury in each group.
- B. The extent of the injury will be analyzed by the size, site and depth of injury.

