 - i. The size of the injury will be measured in centimetres with a sterilized scale.
 - ii. The site of injury can either be the dome of the bladder, the posterior bladder wall, the trigone or one or both ureters.
 - iii. Depth of injury will be taken as layers involved i.e. either involving muscular layer partly or completely with intact mucosa or full depth injury (perforation).
 - iv.

Operative Time: The staff nurse will record the duration of surgery as time in minutes from incision to closure of the skin.

Blood Loss: The estimated blood loss will be determined by the increase in weight of sponges used during the operation, taking 1 gram equal to 1cc of blood and the number of subjects who received blood transfusion during operation.

Secondary Outcomes

Postoperatively, subjects will be assessed for urinary tract infection (UTI), micturition problems, and fistula formation during the hospital stay and for the next three months. Duration of catheterization and hospital stay will also be recorded. The outcome of each subject will be noted on a Performa by assigned medical officers during the hospital stay and the follow-up period and entered in SPSS20 datasheet.

1-Urinary tract infection (UTI) markers will be more than 10pus cells/hpf in urine or urine showing infectious organisms on culture on the third postoperative day.

- A. **Dysuria** will be expressed by the subject as painful micturition using an 11point Numeric Rating Scale ICCs (.673-.825), $r=.7-.99$. (0 No Pain, 1-3 Mild Pain, 4-6 Moderate Pain, 7-10 Severe Pain).
- B. **Other micturition problems** (feeling of incomplete evacuation, frequency, urgency, urethral and extra-urethral incontinence) will be measured subjectively on Likert scale questionnaire (0-never, 1-rarely, 2-sometimes, and 3-often) and analyzed as a composite variable in spss. Urinary retention will be diagnosed if post-micturition bladder volume is >50cc on ultrasonography on the day of discharge from the hospital.

- I. **Feeling of incomplete evacuation:** It is the feeling created by incomplete emptying of the bladder. The subject will be inquired about the feeling of full bladder accompanying it.
- II. **Urgency** will be diagnosed as a sudden urge to urinate.
- III. **Frequency** Needing to pass urine more than seven times in 24hours.

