We will perform Statistical analysis by using IBM spss statistics 20 (SPSS Inc, Chicago, IL, USA). The characteristics of the subjects will be analyzed as continuous data or ordinal data. Normality of continuous data will be analyzed by the Shapiro Wilk test. The normal baseline data will be compared by T-test, non-normal data by Mann Whitney U test and ordinal data with the chi-square test. The outcome of both groups will be calculated as numbers (percentages) by descriptive statistics. The effect of cysto-inflation on outcome data will be analyzed using regression analysis. The same problem experienced by the same subject will be recorded only once on the spss datasheet. There will be no second entry if the subject presents with the same problem again. The data for any subject who do not come for follow up after discharge will be used and analyzed in study characteristics but will be excluded from the analysis of results. The power of the study for bladder injury will be calculated with statistical software G'Power version 3.1.

Adverse events

The study team will be responsible to record all adverse events and serious adverse events to the subjects of the study, related to or not related to the intervention. The team members will ask open probing questions to enhance the quality of the collected data. An adverse event is

defined as any undesirable experience during follow-up leading to contact with the healthcare system (general practitioner or hospital). If adverse event results in hospitalisation, prolonged inpatient hospital care, result in re-surgery, or if an adverse event is life-threatening, result in death, permanent disability or damage, they will be categorised as serious adverse events. Adverse Events will be recorded in the adverse events reporting register. The study team will report all expected and unexpected adverse events in the study population to the principal investigator in monthly meetings to assess their potential consequences.

Data Management Plan

Documents safety

All the documents, together with the numbered envelopes and the completed forms will be stored in folders that will be kept in the locked research office of the principal investigator with access limited to authorised persons. The study team will ensure that all variables from the completed forms are continuously entered into SPSS 20 datasheet.

Data monitoring

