The results of this study will be submitted for publication to an international, peer-reviewed journal, regardless of whether the results are positive, negative or inconclusive concerning the study hypothesis. Authorship eligibility will be based on the recommendations from the International Committee of Medical Journal Editors (ICMJE).

Perspectives of the study

This study is a small, single centred controlled trial. It is among one of the initial studies to test cysto-inflation to prevent bladder injury. If cysto-inflation proves significantly effective in this study, the evidence provided by this study will not be enough in this era of evidence-based medicine. Nevertheless, this research can serve as a foundation to initiate a much larger high-quality multicentre trial in the support of cysto-inflation to prevent bladder injury. This technique if proved effective can also be useful in all fields of pelvic surgery especially urology, urogynecology, and general surgery.

Potential Risks

- Participation in this study poses a risk for breach of confidentiality.
- Catheterization procedure is mandatory in this study. Approximately two out of hundred women may develop a bladder infection. The researchers will use proper sterilization and clean procedure of the insertion of the catheter according to the study protocol to minimize the risk of developing a bladder infection.
- Subjects of the study should not take part in more than one study at the same time as the outcome of the study can be disturbed by this approach.

Problems Anticipated during the study:

- If recruitment of subjects will not be complete during the anticipated study period, then the period of study may be extended from three months to one year or any further time till the recruitment of study is complete.
- In case of any unexpected outcome that may endanger the subject physically or psychologically, the study may be stopped any time.
- As the study is non-funded, the subjects will not be paid for participation in the study. The subjects belonging to the poor socioeconomic group and coming from distant areas will need thorough counselling for compliance to follow up visits.

Acknowledgements: Theatre staff helping in cysto-inflation study will be acknowledged in the publication.

Project Management:

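### Cystoinflation is declared effective on an observed halving of bladder injury alone; no test, interval or significance level governs the verdict

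*Combined protocol and SAP*

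**What the plan says.** The criterion closes the Method paragraph of the Project summary: "Cystoinflation will be considered effective if the proportion of bladder injury in cystoinflation group will be less than 50% of the control". No other sentence in the protocol defines success. Four other places bear on it.

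- **Outcome.** Bladder injury is the first-listed primary outcome and is descriptive: "Bladder injury rate will be recorded as the percentage of subjects with bladder injury in each group". Partial-thickness muscular injury counts as well as perforation.
- **Sample size.** There are 107 women per group, at "95% confidence level and 80% power", with a 10% dropout allowance. No control rate, effect size or sidedness is given. The confidence level belongs to the sizing, not to a decision.
- **Statistical analysis.** "The effect of cysto-inflation on outcome data will be analyzed using regression analysis". The type of regression, the significance level and the interval are not stated, and the 50% criterion is not mentioned. Women who do not return after discharge are to be used "in study characteristics but will be excluded from the analysis of results".
- **Perspectives of the study.** A passing clause, "If cysto-inflation proves significantly effective in this study", names no test or level.

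**The concern.** A threshold on the observed ratio says how large the difference must look. It does not say how unlikely that difference is under chance. When injuries are few, an observed ratio below one half arises easily with no true effect. Followed as written, the plan can declare cystoinflation effective on its leading outcome because of one or a few injuries, while the regression shows nothing. The sponsor hopes the result will found a larger multicentre trial and be useful in other pelvic surgery, so a chance verdict would carry forward.

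**Working it through.** **Inputs.** The rule (observed ratio below 0.5) is from Project summary, and n = 107 per arm from Sample size. Injury rates of 1.17%, 1.94% and 4.49% at the fourth, fifth and sixth caesarean are from Background. Rates of 10% to 30% are assumptions, needed because no rate is given for women with dense adhesions. The 96 per arm is 107 × 0.9 = 96.3.

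**The plan's own figure.** The 107 per group cannot be derived from the stated inputs, because no control rate or effect is given. A standard two-proportion formula for a halving (two-sided 5%, 80% power, no dropout allowance) returns 107 only at a control rate near 33%. A precision formula for one proportion in a population of 400, with an assumed 5% margin and 50% proportion, gives 196.2 in total. That is 196.2 × 1.1 = 215.8, or 107.9 per arm, close to the stated figure, but this formula compares no arms. The sizing therefore does not show what rate was expected.

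**Step 1: single results.** Counts are control v cystoinflation, 107 per arm, with two-sided Fisher p-values.

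| Injuries | Rule met? | p |
|---|---|---|
| 1 v 0 | yes | 1.00 |
| 5 v 2 | yes | 0.45 |
| 5 v 0 | yes | 0.060 |
| 6 v 0 | yes | 0.029 |
| 11 v 5 | yes | 0.19 |
| 21 v 10 | yes | 0.051 |
| 24 v 12 | no | 0.043 |

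With 5 or fewer control injuries, no result that meets the rule is significant. A result can meet it without significance at up to 21 control injuries. From 24 control injuries (24/107 = 22%), a significant reduction can fail the rule.

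**Step 2: how often chance meets the rule.** Let X_c and X_t be independent Bin(n, p), with the same p in both arms. The false-claim rate is P(2·X_t < X_c), summed exactly over all pairs. At p = 1.17% and n = 107 the probabilities of 0, 1 and 2 injuries are 0.2839, 0.3596 and 0.2256. The sum is then:

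- X_t = 0, X_c ≥ 1: 0.2839 × 0.7161 = 0.2033
- X_t = 1, X_c ≥ 3: 0.3596 × 0.1310 = 0.0471
- X_t = 2, X_c ≥ 5: 0.2256 × 0.0087 = 0.0020
- remaining pairs: less than 0.0001

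The total is 0.2524. Across rates, with no true effect:

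| True rate, both arms | Rule met, n = 107 | Of these, Fisher p > 0.05 | Rule met, n = 96 | Rule and Fisher p ≤ 0.05, n = 107 |
|---|---|---|---|---|
| 1.17% | 25.24% | 99.8% | 25.78% | 0.05% |
| 1.94% | 21.41% | 98.8% | 22.32% | 0.26% |
| 4.49% | 13.01% | 92.2% | 14.13% | 1.02% |
| 10% | 4.80% | 69.1% | 5.67% | 1.48% |
| 15% | 1.91% | 28.9% | 2.45% | 1.36% |
| 20% | 0.72% | 3.1% | 1.01% | 0.70% |
| 30% | 0.08% | <0.1% | 0.13% | 0.08% |

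The maximum for the rule alone is 26.5%, near a rate of 0.8%. A two-sided 5% test allows at most 2.5% in this direction. The rule falls to that level at a rate of 13.6% with 107 per arm, or 14.9% with 96. Adding Fisher's test caps the rate at 1.53%, reached near 11.8%.

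**The case against.** The strongest reply is that the sentence sits in a summary, not in Statistical analysis. On that reading 50% is the clinical target and the regression supplies the inference. The reading is reasonable, but the protocol never joins the two, and a verdict of effective can stand beside a non-significant regression.

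Second, the large error rates use general caesarean figures. Enrolment requires "Dense pelvic adhesions of Tulandi score 4 and above" and a bladder that cannot be identified when empty, and partial-thickness injury counts, so the true rate is probably higher. At 20% or 30% the rule is strict. This stands, and it limits the claim: the documents cannot show whether the rule is lax or strict here. Error control should not depend on a rate that nobody has stated.

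Third, injury is seen at surgery, and the follow-up text under Outcome suggests that absentees lose only their post-discharge outcomes. The 96-per-arm column may therefore not apply. Statistical analysis is worded more broadly, so the point is open; the two columns differ little.

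Fourth, Fisher's test alone would control the error (1.5% at a 10% rate, 1.7% at 20%, 1.8% at 30%) and has more power at high rates. Under a true halving at a 30% control rate it succeeds in 70% of trials, against 48% for the joint rule. That is correct. The joint rule is proposed because it keeps the sponsor's own threshold.

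Finally, the arm percentages will be reported, and Background and Perspectives of the study both say that confirmation is needed. This reduces the harm without removing it.

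**Conclusion.** The concern holds. The only stated success criterion has no protection against chance, and nothing elsewhere in the protocol supplies it. With no true effect at 107 per arm, a claim of effectiveness would follow in 13% to 25% of trials at the cited rates of 1.17% to 4.49%. The figure is 4.8% at an assumed 10% and below 1% at 20% or more. These figures assume independent binomial counts and equal true rates in the two arms. Because the rate in the enrolled population is unknown, the false-claim rate is uncontrolled, not known to be high. That a significant reduction short of one half would be called not effective is a lesser point: it is defensible as a minimum relevant effect, but the plan has no wording for that result. The criterion must be amended before unblinding.

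**What to change.** Replace the criterion in Project summary with wording such as: *Cystoinflation will be considered effective if the observed injury proportion is less than 50% of control and the reduction is significant at the two-sided 5% level by Fisher's exact test. The risk difference and risk ratio will be reported with 95% confidence intervals. A significant reduction that does not reach 50% will be reported as a reduction below the target.* State the same rule in Statistical analysis. If an exact test from the planned regression is preferred, name it before unblinding and recompute the figures here, which are for Fisher's test only.

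The change is one of wording in two sections and needs no new data. Its cost is a low chance of success, which should be disclosed. The chance of meeting both conditions at 107 per arm is:

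| Control rate | True ratio 0.5 | True ratio 0.25 |
|---|---|---|
| 4.49% | 6% | 15% |
| 10% | 21% | 54% |
| 15% | 34% | 77% |
| 20% | 44% | 90% |
| 30% | 48% | 98% |

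At a 1.17% control rate it is about 0.1% for a true halving. For a halving it stays below 49% at every control rate up to 60%, because the threshold equals the assumed effect. No claim is possible with 5 or fewer control injuries. The stated 80% power cannot be relied on for a halving, and this amendment does not repair the sample size. If the sponsor values power over the threshold, the alternative is to let Fisher's test decide and report 50% as a target.

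### The only success rule is a bare threshold on the observed injury ratio: a true halving meets it about as often as a coin-flip, and the stated 95% confidence and 80% power do not describe it

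*Combined protocol and SAP*

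**What the plan says.** The one definition of success is in the Project summary, under Method: "Cystoinflation will be considered effective if the proportion of bladder injury in cystoinflation group will be less than 50% of the control". It compares two observed proportions and names no interval, p-value or significance level.

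The Sample size section states that "the sample size is calculated to be 107 for each group at 95% confidence level and 80% power, allowing a 10% drop out rate". It starts from an expectation that "about 400 subjects are expected to present during the study period" and cites "Raosoft, Inc 2004; online sample size calculator for proportions". It gives no control injury rate, effect size or margin of error, and does not refer to the 50% rule.

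The Statistical analysis section plans regression for the effect on outcomes, does not repeat the rule, and leaves the power for bladder injury to be calculated in G*Power. It also removes women without follow-up after discharge from the analysis of results. Perspectives of the study uses the language of significance: "If cysto-inflation proves significantly effective in this study, the evidence provided by this study will not be enough".

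For injury rates, the Background gives figures by caesarean number, the highest being "1.17% for the fourth, 1.94% for the fifth, and 4.49% for the sixth caesarean delivery". It gives none for women with dense adhesions.

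**The concern.** The 50% figure is the only numerical effect criterion in the documents, and it is used as a hurdle for the point estimate. When the true effect equals the hurdle, the estimate falls on either side about equally often, whatever the sample size. When injuries are few, the ratio of two small counts can fall below one half by chance alone. So the rule carries neither the protection against false success that a 95% confidence level suggests nor the sensitivity that 80% power suggests.

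The trial's main verdict is at stake. A useful technique could be reported as not effective, and a reader could take that as a negative result from a study with 80% power. At low injury rates, a useless technique could be reported as effective.

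**Working it through.** **Inputs.** From the documents: 107 per arm; 10% drop-out, so 107 × 0.9 ≈ 96 evaluable; control rates pc of 1.17%, 1.94% and 4.49% (Background). Assumed, because no rate is given for dense adhesions: pc of 10%, 20% and 30%.

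**The plan's own figure.** The 107 cannot be rebuilt as a two-group power calculation without rates. If one assumes a single-proportion precision formula with a 5% margin and 50% response (neither is in the documents) and a population of 400, then n = 400 × 0.9604 / (399 × 0.0025 + 0.9604) = 196.2. Adding 10% gives 215.8, and dividing by 0.9 gives 218.0, i.e. 108-109 per arm. That is close to 107, but power does not enter the formula, and it does not show how 107 was obtained.

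**The rule.** Let C and T be the injuries in the control and cystoinflation arms, independent binomials. With equal arms, the chance of success is the sum of P(C = c) × P(T = t) over all pairs with t < 0.5c. The interval criterion in the last column is success when ln(RR) + 1.96 × SE < 0, with SE² = 1/t − 1/n + 1/c − 1/n and 0.5 added when a count is zero. All entries are for 107 per arm.

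| Control rate | Rule, true halving | Rule, no true effect | 95% CI criterion, true halving |
|---|---|---|---|
| 1.17% | 42.7% | 25.2% | under 0.1% |
| 1.94% | 44.8% | 21.4% | under 0.1% |
| 4.49% | 46.4% | 13.0% | 3.6% |
| 10% | 47.5% | 4.8% | 23% |
| 20% | 48.2% | 0.7% | 52% |
| 30% | 48.4% | 0.1% | 74% |

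- *Sample size.* With 96 per arm the rule gives 46-48% for a true halving at control rates of 4.49-30%. With 1000 per arm it gives 48-49.5% at control rates of about 2-40%.
- *Unequal arms.* With equal arms an exact half is a tie, and a tie fails. At 4.49% a tie has probability 10.8%. With 106 control and 107 cystoinflation women analysed, most such ties become successes and the figure rises to 56.7%. With 107 and 106 it is 46.9%. Over arm sizes from 90 to 107 and control rates of about 2-40%, the highest value found is 57.1%.
- *Effect needed for 80%.* At 107 per arm the rule reaches 80% only if the true risk ratio is about 0.20, 0.30, 0.36 or 0.39 at control rates of 4.49%, 10%, 20% and 30%.
- *Significant results rejected.* For 30 v 16, the ratio is 16/30 = 0.53 and Fisher p = 0.030. For 40 v 20, the ratio is 20/40 = 0.50, which is not below 0.50, and Fisher p = 0.0036. Both fail the rule.
- *False success under the interval criterion.* With no true effect it is under 1% at the three quoted rates.

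**Conventional power for a halving.** Two-sided 5%: power = Φ[(pc − pt − 1.96 s0)/s1], with s0² = 2p̄(1 − p̄)/n and s1² = [pc(1 − pc) + pt(1 − pt)]/n. At 4.49% v 2.245% and n = 107, s0 = 0.02466 and s1 = 0.02462, so power = Φ[(0.02245 − 0.04834)/0.02462] = Φ(−1.05) ≈ 0.146. With n = 96 it is 0.136. Power reaches 80% at a control rate of about 32-33% with 107 evaluable, and about 36% with 96 (0.807).

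**The case against.** A minimum-benefit hurdle is a legitimate choice, and any hurdle is met about half the time when the truth lies exactly on it. The plan never names a halving as the effect to detect, so a failed verdict after a true halving is not plainly a false negative. This stands as far as it goes. It does not supply the missing error control, and it does not stop a reader from attaching the quoted power to the verdict.

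Two stronger readings are tempting, and the documents support neither.

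- A reader might infer that a true halving is called ineffective more often than not at any sample size. That needs exactly equal analysed arms. The exclusion of women lost after discharge can leave the arms unequal, and the chance of success can then pass one half.
- A reader might infer that the 80% power is false. The Sample size section never ties it to the 50% rule. A conventional test would have 80% power for a halving at a control rate of about 32-36%, which the documents neither state nor exclude for dense adhesions.

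It can also be said that an interval criterion is less sensitive where injuries are rare. That is correct, and it is a real cost of the change.

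**Conclusion.** The concern holds in this form: the sole success rule is a point-estimate threshold that matches neither the stated confidence and power nor the planned regression. For a true halving with about 107 per arm it gives 46-48% with equal arms at control rates of 4.49-30%, at most about 57% with slightly unequal arms, and never near 80%. More patients do not cure this. With no true effect, false success runs from 13% to 25% at quoted rates of 4.49% down to 1.17%; it is not a problem at assumed rates of 20% or more, where it is below 1%.

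The 80% therefore cannot be read as the chance of meeting the rule. Whether it holds for a conventional test cannot be settled without a control rate; at 4.49%, the highest rate quoted, power for a halving is about 13-15%. The results assume independent binomial counts and that the rule applies to observed proportions, as its wording says. Rates above 4.49% are assumptions.

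**What to change.** In the Project summary (Method), define effectiveness as a bladder injury proportion lower than in control, with a 95% confidence interval for the risk ratio that excludes 1, and report the observed risk ratio beside the verdict. Carry the same criterion into Statistical analysis. If the sponsor wants the 50% figure as a minimum-benefit criterion, keep it as an additional descriptive criterion and state that failure to meet it is not evidence of no benefit.

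In Sample size, state that the 80% power does not apply to the 50% rule, and give the control rate and effect size for which it does hold.

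The change costs a few sentences and no extra patients or procedures. The downside should be disclosed. At control rates below about 18%, the interval criterion declares success less often than the written rule for a true halving (3.6% v 46% at 4.49%, 23% v 48% at 10%), in exchange for control of false success. Above about 20% it does so more often (74% v 48% at 30%). The verdict would also no longer guarantee that the observed injury rate was at least halved, which is why the observed risk ratio must be reported with it.
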